8.1.2. QTc Stopping Criteria

- The *same* QT correction formula *must* be used for *each individual participant* to determine eligibility for and discontinuation from the study. This formula may not be changed or substituted once the participant has been enrolled.
 - For example, if a participant is eligible for the protocol based on QTcB, then QTcB must be used for discontinuation of this individual participant as well.
 - Once the QT correction formula has been chosen for a participant's eligibility, the *same formula* must continue to be used for that participant *for all QTc data being collected for data analysis*. Safety ECGs and other non-protocol specified ECGs are an exception.
- The QTc should be based on single or averaged QTc values of triplicate electrocardiograms obtained over a brief (e.g., 5-10 minute) recording period.

A participant who meets either bulleted criteria based on the average of triplicate ECG readings will be withdrawn from study treatment:

- QTc > 500 msec OR Uncorrected QT > 600 msec
- Change from baseline of QTc > 60 msec

For patients with underlying bundle branch block, follow the discontinuation criteria listed below:

Baseline QTc with Bundle Branch Block	Discontinuation QTc with Bundle Branch Block
< 450 msec	> 500 msec
450 – 480 msec	≥ 530 msec

See the SoA ([Table 1](#)) for data to be collected at the time of treatment discontinuation and follow-up and for any further evaluations that need to be completed.

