
a. Pre-screening and screening visits may be completed on the same day.
 
b. Agreeing to the genetic sample consent is not required for study participation.
 
c. A pre-screening plasma fibrinogen measurement is only required for participants with 1 COPD exacerbation in the prior year.
 
d. Smoking status /history assessed at screening; smoking status rechecked at Visit 2
 
e. Includes substance usage, past and present medical conditions and family history of premature CV disease.
 
f. See inclusion/exclusion criteria for CXR screening requirement
 
g. Hepatitis B (HBsAg) and Hepatitis C (HepC antibody) testing is required. If testing otherwise performed within 3 months prior to the first dose of study treatment, testing at screening is not required. Hepatitis C RNA testing is optional; however a confirmatory negative Hepatitis C RNA test must be obtained, to be able to enrol participants with positive Hepatitis C antibody due to prior resolved disease.
 
h. Participant's clinical status should be reviewed.
 
i. Pregnancy testing only required for women of child bearing potential (WOCBP). A positive urine pregnancy test requires confirmation with a serum pregnancy test.
 
j. E-RS:COPD is a subset of EXACT-PRO and is not a separate assessment.
 
k. Rescue medication use will be assessed via e-diary and MDI sensor.
 
l. The Clinic Visit PROactive Physical Activity in COPD tool will be assessed in a subset of approximately 50% of study participants
 
m. Pre-dose PK samples will be collected in all participants at Visits 3, 6, 7, and 10. In a subset of participants (approx. 50 participants at each dose level) at Visit 3, PK samples will be collected at pre-dose, 0.5, 1, 2, 4, 6, 8, 10, 12 hours post-dose. In a subset of participants (approx.. 50 participants at each dose level) at Visit 10, PK samples will be collected at pre-dose, 0.5. 1. 2. 4. 6, 8, 10, 12 hours post-dose.
													

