8. History or current evidence of other clinically significant medical condition that is uncontrolled on permitted therapies. Significant is defined as any disease that, in the opinion of the Investigator, would put the safety of the participant at risk through study participation, or that would affect the safety analysis or other analysis if the disease/condition worsened during the study.
9. Current or chronic history of liver disease, or known hepatic or biliary abnormalities (with the exception of Gilbert's syndrome or asymptomatic gallstones).
10. Abnormal and clinically significant 12-lead ECG finding. The investigator will determine the clinical significance of each abnormal ECG finding in relation to the participant's medical history and exclude participants who would be at undue risk by participating in the study. An abnormal and clinically significant finding that would preclude a participant from entering the study is defined as a 12-lead tracing that is interpreted as, but not limited to, any of the following:
 - a. AF with rapid ventricular rate > 120 bpm
 - b. sustained or non-sustained VT
 - c. second degree heart block Mobitz type II and third degree heart block (unless pacemaker or defibrillator has been implanted)
 - d. QTcF ≥ 500 msec in participants with QRS < 120 msec and QTcF ≥ 530 msec in participants with QRS ≥ 120 msec
11. Previous lung surgery (e.g. lobectomy, pneumonectomy) or lung volume reduction procedure.

Prior/Concomitant Therapy

12. Current or expected chronic use of macrolide antibiotics during the study period for the prevention of COPD exacerbations. Examples of chronic use include, but are not limited to, daily or two to three times per week use for at least 3 months.

13. Oral or injectable CYP3A4 or BCRP (breast cancer resistance protein) substrates with a narrow therapeutic index (CYP3A4 substrates include, but are not limited to, alfenatil, cyclosporine, dihydroergotamine, ergotamine, fentanyl, pimoziide, quinidine, sirolimus, tacrolimus, and theophylline; BCRP substrates include, but are not limited to, topotecan.) The Investigator should consult with the Medical Monitor if necessary.
14. Current or expected use of phosphodiesterase-4 inhibitors (e.g. roflumilast). Participants currently receiving roflumilast may be included if they are able to discontinue use from 30 days prior to screening through the completion of the follow up visit.

Prior/Concurrent Clinical Study Experience

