9.4.3. Electrocardiograms

- For participant screening and pre-dose on Day 1, triplicate ECG measurements should be collected. For all subsequent ECG assessments, single measurement are to be collected. 12-lead ECG will be obtained as outlined in the SoA using an ECG machine that automatically calculates the heart rate and measures PR, QRS, QT, and QTc intervals. Refer to Section 8.1.2 for QTc withdrawal criteria and additional QTc readings that may be necessary.
- At each time point at which triplicate ECG are required, 3 individual ECG tracings should be obtained as closely as possible in succession, but no more than 2 minutes apart. The full set of triplicates should be completed in less than 5 minutes.

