### 5.2. Baseline Definitions

Any assessments made after the start of study treatment will not be included in the derivation of baseline. Assessments made on the same day as the start of treatment are assumed to be taken prior to first dose.

If baseline data are missing, no derivation will be performed and baseline will be set to missing.

Parameter	Baseline Used in Data Display
E-RS: COPD total and subscale scores	Mean score during a stable period between (Latest of (7 days before Study treatment start date (Day 1) and day of Visit 1 (Screening)) and day before Day 1 of study treatment. Data must be present on at least 4 days
EXACT (for determining EXACT events)	Defined according to the EXACT User Manual v8.0 ( Evidera, 2016a )
SGRQ total and domain scores	Day 1
CAT score	Day 1
Rescue use (diary card and sensor data, mean number of puffs/occasions per day and percentage of rescue-free days)	Mean score during a stable period between (Latest of (7 days before Study treatment start date (Day 1) and day of Visit 1 (Screening)) and day before Day 1 of study treatment. Data must be present on at least 4 days.
PROactive score	A PROactive Total Score and two domain scores (amount and difficulty) will be derived using data from the C-PPAC questionnaire on Day 1 and physical activity

Parameter	Baseline Used in Data Display
	monitor worn between Visit 2 and Visit 3 (7 days). The activity monitor must have been worn for at least 3 days with $\geq 8$ hours wearing (the 3 days do not need to be consecutive). Further details of the derivation are described in Section 14.6.3 and in the IMI PROactive user manual (14JUN16).
Blood pressure (BP)	Latest pre-dose assessment with a non-missing value for both systolic and diastolic BP, including those from unscheduled visits
Pulse rate, laboratory data, ECG	Latest pre-dose assessment with a non-missing value for the individual assessment, including those from unscheduled visits
Post-bronchodilator (BD) FEV1, post-BD FVC	Day 1

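### With QRS ≥120 msec, QTcF 501–529 msec passes exclusion 10d but already exceeds the mandatory QTc >500 msec stopping limit

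*Protocol*

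**What the plan says.** **Entry.** Protocol Section 6.2, exclusion 10d, uses two limits that depend on QRS width. With QRS below 120 msec, exclusion starts at QTcF 500 msec. The other limit is "QTcF ≥ 530 msec in participants with QRS ≥ 120 msec".

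**Stopping.** Protocol Section 8.1.2 lists two general criteria. The first is "QTc > 500 msec OR Uncorrected QT > 600 msec"; the second is a rise of more than 60 msec from baseline. The consequence is not optional: "A participant who meets either bulleted criteria based on the average of triplicate ECG readings will be withdrawn from study treatment". QRS width is not mentioned.

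**The exception.** A short table follows, introduced by "For patients with underlying bundle branch block, follow the discontinuation criteria listed below". It has two rows. A baseline below 450 msec stops above 500 msec, and a baseline of 450 to 480 msec stops at 530 msec or more. There is no row above 480 msec.

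**Scale and timing.** Section 8.1.2 requires one correction formula per participant for both eligibility and discontinuation. Section 9.4.3 says "For participant screening and pre-dose on Day 1, triplicate ECG measurements should be collected"; later scheduled ECGs are single recordings.

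**The concern.** An entry limit and a stopping limit on the same measurement should leave no one both admissible and due to stop. Here they are keyed to different things: the relaxed entry limit to QRS width, the relaxed stopping limit to BBB. The figure 530 appears in both, but in the stopping table only for BBB baselines of 450–480 msec.

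Two consequences follow. A wide-QRS participant without BBB can enter with a QTc that the stopping rule does not tolerate, and can then lose treatment although nothing has changed since entry. For a BBB participant whose baseline is above 480 msec, the table the site is sent to is silent, so two sites could apply different limits to the same tracing. What is at stake is consistent safety conduct and a few uninformative discontinuations.

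**Working it through.** The plan states no figure to reproduce. The check sets the rules side by side in whole milliseconds.

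**Inputs.** Entry limits come from Section 6.2 (10d). The general stop and the BBB table come from Section 8.1.2.

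**1. Narrow QRS (<120 msec).** The highest admissible QTcF is 499 and the lowest stopping value is 501. The two do not overlap, so the rules fit.

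**2. Wide QRS (≥120 msec), no BBB.** The highest admissible QTcF is 530 − 1 = 529. The lowest stopping value is 501. The overlap is 501 to 529, which is 529 − 501 + 1 = 29 values, exceeding the limit by 1 to 29 msec. Exactly 500 is admissible and does not stop.

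**3. Wide QRS with BBB.** The last table row ends at 480 and entry runs to 529, so baselines without a row are 481 to 529: 529 − 481 + 1 = 49 values. Suppose the general criteria are the default:

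- 481–500 (20 values) is workable. Headroom to the first stopping value runs from 501 − 481 = 20 msec down to 501 − 500 = 1 msec. The change rule would first act at baseline + 61, that is 542 to 561, so the absolute limit always acts first.
- 501–529 (29 values) has the same conflict as in step 2.

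**4. Could the scales differ?** No. The formula that qualified the participant must also be used for stopping.

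**5. Does the SAP reconcile the limits?** No. SAP Section 14.8.2 flags absolute QTc above 530 msec as potentially clinically important. That is a reporting range and does not alter Section 8.1.2.

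**6. Effect of the proposed entry limit (QTcF ≥500 excluded at any QRS width).** The highest admissible value becomes 499, below 501, so the overlap is empty. BBB baselines of 481–499 still have no row, which is why a sentence after the table is also needed. Wide-QRS values removed from eligibility are 500 to 529: 530 − 500 = 30 values. Of these, 29 are above the general stopping limit and one (exactly 500) is not.

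These counts measure the width of the overlap. They do not count participants.

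**The case against.** **Discretion already covers it.** Exclusion 10 says its ECG list is not exhaustive and tells the investigator to keep out anyone at undue risk. Section 8.2 allows withdrawal for safety, and Section 9 directs urgent concerns to the sponsor. This stands in part: the protocol permits entry at 501–529 msec but does not require it. None of these provisions supplies a number, however, and Section 9 rules out waivers, so a site cannot simply set the stop aside for someone it has admitted.

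**One ECG at Day 28 does not force withdrawal.** A reader might infer that the first scheduled on-treatment ECG (Visit 5) would end treatment. The text does not support that. Withdrawal needs a triplicate average, and Section 9.4.3 provides for extra readings. A stable participant at this level would also show it on the Day 1 pre-dose triplicate. The objection stands; the consequence is withdrawal on a confirming triplicate.

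**The general criteria can serve as the default for BBB.** They are addressed to any participant, so a reader who concludes that all BBB baselines of 481–529 msec have no workable limit goes too far. On the default reading 481–500 is usable and needs only a clarifying sentence.

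**Drift between screening and Day 1.** One could argue that a BBB participant screened at 475 msec and measured at 485 msec on Day 1 falls out of the table, because SAP Section 5.2 defines the ECG baseline as "Latest pre-dose assessment with a non-missing value for the individual assessment, including those from unscheduled visits". That section defines baselines for data displays. It does not tell sites which value to use in Section 8.1.2, so the argument is not supported. It is also unnecessary, since 10d admits a screening value of 485 msec directly.

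**Conclusion.** The two rules contradict each other as written for QRS ≥120 msec without BBB at 501–529 msec, and no other section reconciles them. For BBB the table is incomplete above 480 msec. If the general criteria are the default, the real conflict is again 501–529 msec; the protocol does not state that default.

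The conclusion assumes whole-millisecond values and that some wide-QRS participants do not have BBB. The documents do not say how many participants fall in the range; the number is probably small. The matter is one of safety conduct and leaves the E-RS:COPD primary endpoint and the power untouched. It is a minor correction, but a mandatory stopping rule should not already be met by someone the protocol admits.

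**What to change.** 1. **Section 6.2, exclusion 10d:** exclude QTcF ≥500 msec regardless of QRS width.
2. **Section 8.1.2, after the table:** state that newly enrolled BBB participants with a baseline QTc above 480 msec follow the general criteria.
3. **Already enrolled with a baseline above 500 msec:** the medical monitor sets and documents an individual limit. Write this into the amendment, so that it is a protocol rule and not a waiver. Without it, the clarified text would itself force these participants out with no drug signal.

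**Cost.** One revised exclusion item and short added text in a protocol amendment. No ECG is added: pre-dose triplicates are already scheduled, "using an ECG machine that automatically calculates the heart rate and measures PR, QRS, QT, and QTc intervals".

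**Downside.** A few wide-QRS participants at 500–529 msec lose eligibility, nearly all of them already above the general stopping limit. The BBB limit would also step down at a baseline of 480 msec. At 480 the stop is 530 msec (headroom 530 − 480 = 50 msec); at 481 the first stopping value is 501 msec (headroom 20 msec). The medical team should confirm that this step is intended.

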8.1.3. Neutrophil Stopping Criteria

A participant with a peripheral blood neutrophil count $\leq 0.5 \times 10^9/L$ that is confirmed on repeat testing will be instructed to suspend dosing. The neutrophil count should be monitored daily until it returns to within the baseline value, as detailed in [Appendix 9](#).

8.1.4. Temporary Discontinuation

Temporary discontinuation of study treatment is allowed for up to 14 days when medically necessary, e.g. for hospitalization for a COPD exacerbation, other medical

condition requiring hospitalization, or reduction in peripheral blood neutrophil counts $\leq 0.5 \times 10^9/L$. Temporary discontinuation for any other reason should be discussed with the GSK Medical Monitor.

8.1.5. Study Treatment Restart

Study treatment restart after liver chemistry stopping criteria are met by any participant in this study is not allowed. Refer to [Appendix 7](#) for full guidance for required actions and follow-up assessments to undertake if liver stopping criteria are met.

Study treatment restart after neutrophil stopping criteria are met can be considered once the neutrophil count has returned to within baseline and provided that no more than 14 days have elapsed since study medication was halted. The Investigator must obtain approval from the GSK Medical Monitor prior to restarting study treatment. See [Appendix 9](#) for the procedure to be followed for study treatment restart after neutrophil stopping criteria are met.

8.2. Withdrawal from the Study

- A participant may withdraw from the study at any time at his/her own request, or may be withdrawn at any time at the discretion of the investigator for safety, behavioural, compliance or administrative reasons.
- If the participant withdraws consent for disclosure of future information, the sponsor may retain and continue to use any data collected before such a withdrawal of consent.
- If a participant withdraws from the study, he/she may request destruction of any samples taken and not tested, and the investigator must document this in the site study records.
- Refer to the SoA for data to be collected at the time of study discontinuation and follow-up and for any further evaluations that need to be completed.

8.3. Lost to Follow Up

A participant will be considered lost to follow-up if he or she repeatedly fails to return for scheduled visits and is unable to be contacted by the study site.

The following actions must be taken if a participant fails to return to the clinic for a required study visit:

- The site must attempt to contact the participant and reschedule the missed visit as soon as possible and counsel the participant on the importance of maintaining the assigned visit schedule and ascertain whether or not the participant wishes to and/or should continue in the study.
- Before a participant is deemed lost to follow up, the investigator or designee must make every effort to regain contact with the participant (where possible, 3 telephone calls and, if necessary, a certified letter to the participant's last known

mailing address or local equivalent methods). These contact attempts should be documented in the participant's medical record.

- Should the participant continue to be unreachable, he/she will be considered to have withdrawn from the study with a primary reason of lost to follow-up.

9. STUDY ASSESSMENTS AND PROCEDURES

- Study procedures and their timing are summarized in the SoA ([Table 1](#)).
- Protocol waivers or exemptions are not allowed
- Immediate safety concerns should be discussed with the sponsor immediately upon occurrence or awareness to determine if the participant should continue or discontinue study treatment.
- Adherence to the study design requirements, including those specified in the SoA, is essential and required for study conduct.
- All screening evaluations must be completed and reviewed to confirm that potential participants meet all eligibility criteria. The investigator will maintain a screening log to record details of all participants screened and to confirm eligibility or record reasons for screening failure, as applicable.
- Procedures conducted as part of the participant's routine clinical management (e.g., blood count) and obtained before signing of ICF may be utilized for screening or baseline purposes provided the procedure met the protocol-specified criteria and was performed within the time frame defined in the SoA.
- The maximum amount of blood collected from each participant over the duration of the study, including any extra assessments that may be required, will not exceed 500 mL.
- Repeat or unscheduled samples may be taken for safety reasons or for technical issues with the samples.

9.1. Efficacy Assessments

9.1.1. EXACT and E-RS:COPD

The Exacerbations of Chronic Pulmonary Disease Tool (EXACT) is a 14 item patient reported outcome instrument designed to capture information on the occurrence, frequency, severity, and duration of exacerbations of disease in patients with COPD [[Jones, 2011](#); [Leidy, 2010](#); [Leidy, 2011](#)]. EXACT captures information on the severity of the respiratory and systemic manifestations of a COPD exacerbation as reported by the patient. The instrument is to be completed daily (typically at bedtime) using an electronic diary. The daily recording of information allows an assessment of underlying day to day variability of a patient's symptoms and facilitates the detection of symptom worsening indicative of a COPD exacerbation. The total score for EXACT ranges from 0 – 100, higher scores indicate more severe symptoms. The entire instrument is intended to be completed in about 3 minutes or less (typically the time required for completion decreases as the patient becomes more familiar with the tool and the electronic diary).

The Evaluating Respiratory Symptoms in COPD (E-RS:COPD) tool consists of 11 items from the 14 item EXACT instrument [Leidy, 2014a; Leidy, 2014b]. E-RS:COPD is intended to capture information related to the respiratory symptoms of COPD, i.e. breathlessness, cough & sputum production, chest tightness and chest congestion. E-RS:COPD has a scoring range of 0 – 40, higher scores indicate more severe symptoms. Three subscales of E-RS are used to describe different symptoms, dyspnea, cough and sputum, and chest symptoms.

E-RS: COPD has recently been recognized as a drug development tool by FDA and EMA [EMA, 2015; FDA, 2016].

9.1.2. COPD Exacerbations

An exacerbation of COPD is defined by a worsening of symptoms.

The following are symptoms used to determine an exacerbation of COPD:

Worsening of two or more of the following major symptoms for at least two consecutive days:

- Dyspnea
- Spontaneous sputum volume
- Sputum purulence

OR

Worsening of any one of the above major symptoms together with any one of the following minor symptoms for at least two consecutive days:

- Sore throat
- Cold (nasal discharge and/or nasal congestion)
- Fever (oral temperature > 37.5 °C) without other cause
- Increased cough
- Increased wheeze

Participants who experience worsening COPD symptoms for greater than 24 hours should:

- Contact their study investigator and/or research coordinator as soon as possible and report to the study clinic as required
- If the participant is unable to contact their study investigator or research coordinator, they should contact their primary care provider (or other health care provider) and contact their study site as soon as possible
- Continue to record their symptoms and rescue medication use in their daily diary

- If the participant seeks emergency/acute care for worsening respiratory symptoms he/she should request the caring health care provider to contact the study investigator or research coordinator as soon as possible
- COPD exacerbations will be classified according to severity as follows:
- A COPD exacerbation is defined as a mild exacerbation if it is self-managed by the participant. Mild exacerbations are not associated with the use of antibiotics and/or systemic corticosteroids
- A COPD exacerbation is defined as a moderate exacerbation if it requires a new prescription for antibiotics and/or systemic corticosteroids
- A COPD exacerbation is defined as a severe exacerbation if it requires hospitalization, an emergency room visit, or extended observation in an outpatient centre

Details of an exacerbation should be recorded in the exacerbation page of the eCRF. Exacerbations will not be reported according to the standard process for expedited reporting of SAEs to GSK (even though the event may meet the definition of an SAE) as they are considered Disease Related Events (DREs). Only when the event is, in the Investigator's opinion, of greater intensity, or duration than expected for the individual participant, or the Investigator considers that there is a reasonable possibility that the event is related to study treatment should it be reported as an SAE (See Section 9.2). (Pneumonia must be recorded in the AE or SAE section of the eCRF and on the pneumonia page of the eCRF (See Section 9.4.5)).

All medications used for the treatment of exacerbations must be recorded in the source documents and the exacerbation page of the eCRF. If necessary, the PI or other health care personnel may stop the participant's study treatment temporarily in order to treat the COPD exacerbation. The reason for temporarily stopping study treatment and duration should be recorded in the eCRF.

The date of onset and the date of resolution will be recorded in the source documents and the eCRF.

- The date of onset is the first day (of at least 2 consecutive days) or worsening symptoms described above.
- The date of resolution should be based on when the Investigator or participant determines that the COPD symptoms have returned to near pre-exacerbation levels or to a new baseline.

